We will perform a retrospective cohort study to compare VTE risk and VTE risk factors in adults with IBD, RA, and PsA and matched controls between January 1, 1998 and January 1, 2018, within the RCGP RSC network. In the cohorts with and without inflammatory conditions we will estimate the risk of VTE overall, and for PE and DVT separately, using unadjusted Cox proportional hazards models, stratified by matched set (exposed cohort versus unexposed cohort), to provide overall hazard ratios for the association with each outcome. Models will be subsequently adjusted for sociodemographic and clinical and VTE risk factors in multivariable analysis to explore potentially important associations with VTE. We will then repeat the same analyses for each autoimmune condition separately. We will perform prespecified sensitivity analyses to explore the robustness of any potential associations.

Lay summary

Blood clots occurring in the legs and in the lungs are relatively common; they occur in around 3 in a 1000 people per year. They can cause disability and are also potentially life threatening. When a clot occurs in the legs it is called a deep vein thrombosis or DVT. When they occur in the lungs they are called a pulmonary embolism or PE. The risk for DVT and PE is higher in people with conditions which cause inflammation. The most common of these are inflammatory bowel disease (ulcerative colitis and Crohn's disease), rheumatoid arthritis, and psoriatic arthritis (a condition comprised of psoriasis and joint inflammation).

What is not known is how much higher the risk of DVT and PE is in these groups compared with people without inflammatory disease, and what causes the excess risk in these people. This study aims to assess the measure the exact increase in risk for DVT and PE in people with these inflammatory conditions and to identify which risk factors are most strongly associated with the increased risk. These data should help us understand the causes of blood clot risk in these inflammatory conditions and identify targets for reducing risk.

Introduction

Venous thromboembolism (VTE), comprising pulmonary embolism (PE) and deep vein thrombosis (DVT), is relatively common, with an incidence in the general population of around 3 cases per 1000 patient years.¹ It is associated with significant morbidity and mortality.

Systemic inflammation is a risk factor for VTE,² and risk of VTE has been shown to be increased amongst individuals with chronic inflammatory conditions including inflammatory bowel disease (IBD) and rheumatoid arthritis (RA) compared to the general population.³⁻⁶ Evidence for differential VTE risk in other inflammatory diseases, notably psoriatic arthritis (PsA) and vasculitis, is more limited.⁴ Risk factors for VTE have been described in the general population, and include C-reactive protein (CRP), obesity, fractures, surgery and use of oral corticosteroids and hormone therapy,^{7, 8} but there has been little interrogation of patterns of VTE risk factors for individuals with chronic inflammatory conditions and their association with subsequent VTE.⁹

In this context we will set out to describe the prevalence of VTE risk factors in individuals with systemic inflammatory disorders in a contemporary real-world population, by disease type (IBD, RA, and PsA) and relative to a control population without systemic inflammatory disease. In the same cohorts we will further compare the influence of VTE risk factors on risk of VTE events in individuals with systemic inflammatory disorders.

Methods

Study design

We will perform a retrospective cohort study to compare VTE risk and VTE risk factors in adults with IBD, RA, and PsA and matched controls between January 1, 1998 and January 1, 2018, using a large UK primary care database.

Data source

The Royal College of General Practitioners Research (RCGP) and Surveillance Centre (RSC) database will be used for this study. The RCGP RSC cohort derives from a large network of GP

practices distributed across England and provides representative sample of the UK population.¹⁰

The RCGP RSC database contains information on clinical diagnoses, anthropometric measurements (e.g., body mass index; BMI), laboratory tests results, and prescriptions, coded with the Read coding system (a thesaurus of clinical terms).¹¹ UK general practice lends itself to this type of study because it is a registration-based system (each patient can only be registered with a single GP), it has been computerised since the 1990s, and pay-for-performance targets introduced in 2004 have resulted in consistent high-quality clinical data entry about chronic disease.¹² All RCGP RSC registered practices have electronic laboratory links; meaning all test results are automatically coded and uploaded to the GP computer system. Studies using RCGP RSC data have been published across a range of chronic diseases.¹³⁻¹⁵

Study population

Adult patients (aged ≥18) contributing to RCGP RCS primary care database between January 1, 1998 and January 1, 2018, will be eligible for inclusion.

Definition of the exposed cohort with systemic inflammatory disease

The exposed cohort will include all individuals with an existing or incident diagnosis of IBD, RA or PsA (systemic inflammatory diseases) in the RCGP RCS over the study period. IBD, RA or PsA will be identified using Read diagnostic codes previously validated in UK primary care studies.¹⁶⁻¹⁸ Follow-up for exposed individuals will begin on the latest of the date of diagnosis indicated by first diagnostic code, January 1 1998 or 180 days after practice registration.

Definition of the matched unexposed cohort

The matched unexposed cohort will be defined by matching individuals in the exposed cohort with individuals who were never diagnosed with a systemic inflammatory disease either prior to or during the study period by age and sex at GP practice level. Unexposed individuals will require at least one year of follow-up when matched to minimise the risk they had a nonrecorded existing diagnosis of a systemic inflammatory disease of interest. Follow-up for each matched individual will begin at the start of follow-up of their exposed counterpart.

Follow-up will end at the earliest of the study end-date (January 1, 2018), the date of patient transfer from an included practice, date of death, or the date an individual developed an outcome of interest.

Outcomes

The pre-specified outcomes include the time to incident VTE (either PE or DVT), time to PE, and time to DVT. These outcomes will be defined using Read codes that have been previously validated in a similar UK primary care database.¹⁹ Time to each outcome will be compared between individuals with a systemic inflammatory disorder and the matched control population, and across IBD, RA and PsA subgroups.

Baseline characteristics and VTE risk factors

Baseline measures will comprise sociodemographic characteristics, clinical features and biomarkers, selected based on clinical expertise and existing literature demonstrating an established association with VTE or evidence to support an association with VTE among individuals with systemic inflammatory disorders.^{4, 7} Socioeconomic status will be defined using the official national measure; the index of multiple deprivation (IMD).²⁰ This will be calculated at the point of data extraction, using patient postcode, with the resultant scores stratified by deprivation quintile. Ethnicity will be extracted from the primary care record and grouped into the major UK ethnic groups; white, black, Asian, mixed, and others.²¹ BMI will be defined as the most recently recorded measurement prior to the study start date. Smoking status and alcohol use will be defined using the most recently recorded data prior to the study start date. Diagnostic codes will be used to define the presence of comorbidities at baseline: hypertension, hyperlipidaemia, diabetes, peripheral vascular disease, cardiovascular disease (Atrial fibrillation, angina, myocardial infarction, congestive heart failure), cerebrovascular disease, cancer, chronic obstructive pulmonary disease, chronic kidney disease (stages 3–5), liver disease, recent hospitalisation, joint replacement, and fractures. Diabetes and diabetes type will be identified using an algorithm developed for use within the RCGP RSC database.²²

The Read codes used to describe cardiovascular disease within the RCGP RSC database have been previously reported.^{23, 24} We will also extract records of pregnancy and reduced mobility. Biomarkers and laboratory tests including cholesterol and blood pressure will be derived by taking the most recent value in the year before cohort entry.

We will examine the following medications commonly used for the management of systemic inflammatory disorders: non-steroidal anti-inflammatory drugs (NSAIDs), oral corticosteroids, disease modifying anti-rheumatic drugs (DMARDs), other non-biologic immunosuppressant medications, and biologic therapies (where recorded). We will also include hormone therapy (hormonal contraceptives, hormone replacement therapy). We will also extract information on prescribing of antiplatelet agents (aspirin or adenosine diphosphate receptor inhibitors) and lipid lowering therapy (statins, fibrates, or ezetimibe). Prescribing at the study start date will be defined as the presence of an issued prescription in the three months preceding or one month after the date of diagnosis.

Statistical Analyses

We will describe the characteristics at baseline for individuals with IBD, RA and PsA separately in comparison to the matched unexposed cohort. We will evaluate differences in characteristics at entry between those with and without systemic inflammatory disease using the χ^2 test for categorical variables and the unpaired t-test for continuous data. All reported *P*-values will be two-sided.

Event rates for the primary and secondary outcomes will be compared in individuals with and without systemic inflammatory disease, calculated as the number of events divided by the total person-years of follow-up, and expressed as the number per 1000 person-years.

Risk of VTE

We will estimate the risk of VTE overall, and for PE and DVT separately, using unadjusted Cox proportional hazards models, stratified by matched set (exposed cohort versus unexposed cohort), to provide overall hazard ratios for the association with each outcome. Models will be subsequently adjusted for sociodemographic and clinical and VTE risk factors in

multivariable analysis. We will then repeat the same analyses for each autoimmune condition separately.

Predictors of VTE

Subsequently, we will run multivariable Cox models to examine the relative influence of individual VTE risk factors in the cohort with systemic inflammatory disease and control cohort. We will then explore the impact of changing platelet count over the study follow-up on VTE risk by including platelet count as a time varying exposure in survival models.

Sensitivity analysis

To check the sensitivity of findings to the date of introduction of the quality and outcomes framework (QOF), we will repeat the main analyses with the study follow-up for exposed individuals beginning on the latest of the date of diagnosis indicated by first diagnostic code, January 1 2004 or 180 days after practice registration.

All statistical analyses will be performed in R statistical package.

Ethics approval

Study approval will be requested from the Research Committee of the RCGP RSC. The study does not meet the requirements for formal ethics board review as defined using the NHS Health Research Authority research decision tool (http://www.hra-decisiontools.org.uk/research/).

Contributors

Research support for this project in several areas including data analysis, literature searching, and medication writing will be provided by Momentum Data. [name] and [name] of Momentum Data have contributed to the writing of this protocol and to the study design. Funding for these studies has been provided by Pfizer UK.

Scientific rigor and study registration

The team ethos at Momentum Data is to support the highest quality research, for patient benefit, with rigorous scientific standards. Publication bias remains an issue in observational studies. Therefore, if approval is granted the protocol will be registered as an observational study with ClinicalTrials.gov and made publicly available prior to the commencement of data analysis. Any protocol amendments will be published alongside this public record of the study and will be noted in any final publication with the rationale for the modification. Any changes will be assessed for the need for ethics approval and further RCGP RSC study approval; these will be sought if required.

References

3. Choi HK, Rho Y-H, Zhu Y, Cea-Soriano L, Aviña-Zubieta JA, Zhang Y. The risk of pulmonary embolism and deep vein thrombosis in rheumatoid arthritis: a UK population-based outpatient cohort study. *Annals of the Rheumatic Diseases* 2013; **72**(7): 1182-7.

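### Follow-up starts and ends on patient-level and study-wide dates only; without practice-specific recording dates, any unrecorded practice time dilutes the VTE rates, by an unknown amount

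*Combined protocol and SAP*

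**What the plan says.** Under the definition of the exposed cohort, follow-up starts on "the latest of the date of diagnosis indicated by first diagnostic code, January 1 1998 or 180 days after practice registration". Under the definition of the matched unexposed cohort, "Follow-up for each matched individual will begin at the start of follow-up of their exposed counterpart". The end rule is in the same section: "Follow-up will end at the earliest of the study end-date (January 1, 2018), the date of patient transfer from an included practice, date of death". An outcome event also ends follow-up.

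The Study population section sets eligibility: "Adult patients (aged ≥18) contributing to RCGP RCS primary care database between January 1, 1998 and January 1, 2018, will be eligible for inclusion". On the recording of long-term conditions, the Data source section says of UK general practice that "it has been computerised since the 1990s, and pay-for-performance targets introduced in 2004 have resulted in consistent high-quality clinical data entry".

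Under Statistical Analyses, event rates are "calculated as the number of events divided by the total person-years of follow-up, and expressed as the number per 1000 person-years". The baseline section defines comorbidities by the presence of a diagnostic code and current prescribing by an issued prescription near the date of diagnosis. BMI and laboratory values come from the most recent earlier measurement. The Sensitivity analysis section repeats the main analyses with the common calendar start moved from 1998 to 1 January 2004.

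**The concern.** A primary care database can show a VTE only while the practice is recording it and sending it. The rules start and stop each person's clock on that person's own dates or on two dates common to the whole study. No rule asks whether the practice's coded record was usable at entry, or whether data were still arriving at exit. A patient whose practice stops sending data has neither transferred nor died, so as written that patient accrues event-free time to 1 January 2018.

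Two outputs are exposed. The first is the rate per 1000 person-years, where unrecorded time adds to the denominator and little or nothing to the numerator. The second is the baseline prevalence of VTE risk factors, which is part of the study's stated objective. For items defined by a code or a prescription, a thin early record looks the same as absence. The protocol gives grounds to ask the question: it credits consistent recording to 2004, yet opens its main analysis in 1998.

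**Working it through.** **Reading the rules.** The start rule has three dates: first diagnostic code, 1 January 1998, and registration plus 180 days. The end rule has four: 1 January 2018, transfer, death and outcome. The two calendar dates are study-wide and the rest belong to the patient. None marks when a practice's record became usable or when its last data were collected. The 2004 rerun replaces one study-wide start date with another and leaves the end rule alone.

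**Which outputs each gap affects.**
- Start side: rates, and baseline items defined by presence of a code or prescription. BMI and biomarkers would be missing, not falsely absent.
- End side: rates only. A practice that stops sending data later cannot change what was recorded at baseline.

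**Size.** The plan reports no event count, person-time or practice dates, so there is no figure of its own to reproduce. Let *f* be the share of person-time in periods when the practice is not fully recording, and *s* the share of VTEs still captured there. Then

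reported rate = true rate × (1 − *f*(1 − *s*)).

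The true rate is set at 3.0 per 1000, the general-population figure in the protocol's Introduction, for illustration only. Both *f* and *s* are assumptions.

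| *f* | *s* = 0 | *s* = 0.5 | *s* = 0.8 |
|---|---|---|---|
| 5% | 3.0 × 0.95 = 2.85 | 3.0 × 0.975 = 2.925 | 3.0 × 0.99 = 2.97 |
| 10% | 3.0 × 0.90 = 2.70 | 3.0 × 0.95 = 2.85 | 3.0 × 0.98 = 2.94 |
| 15% | 3.0 × 0.85 = 2.55 | 3.0 × 0.925 = 2.775 | 3.0 × 0.97 = 2.91 |

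The understatement is *f*(1 − *s*). It runs from 1% (5% affected, 80% captured) to 15% (15% affected, none captured).

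**Hazard ratio.** Matching is within practice, the pair shares a start date, and the Cox model is stratified by matched set. An unrecorded period therefore falls at the same follow-up times for both members. The partial likelihood uses only times at which an event is recorded, so a period with none contributes nothing.

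A simulation of 2,000,000 matched sets bears this out. All its settings are assumed: 1:1 matching, true rates of 4.5 and 3.0 per 1000 (ratio 1.5), follow-up of 2-20 years and 5% yearly loss. In 30% of sets, 0-6 years at the start and 0-5 years at the end went unrecorded.
- Share of control person-time unobservable: 14.7%.
- Rates under the written rules: 3.83 exposed, 2.56 unexposed. The formula with *f* = 0.147 and *s* = 0 agrees for the controls: 3.0 × 0.853 = 2.56.
- Rates with person-time cut to the practice's recording window: 4.49 and 3.00.
- Stratified hazard ratio under the written rules: 1.505, against a true 1.50.

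**The case against.** The strongest reply is that the start rule partly corrects itself. One of its three dates is the first diagnostic code. If a practice's coded record begins in 2000 and nothing was back-entered, no exposed person there can enter before 2000, and controls inherit that date. Early entry needs a diagnosis back-entered with its original date, and a practice that did this may have back-entered past VTEs and comorbidities too. This stands. It makes the start-side gap conditional, and it is why partial capture belongs in the calculation.

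Second, the 2004 rerun is a prespecified check on early under-recording. This also stands. A reader might infer much larger losses from a single 1998 entrant. With 5-10% yearly attrition (assumed), the share of that person's person-years falling before 2000 is (1 − e^−0.1)/(1 − e^−1) = 15.1% to (1 − e^−0.2)/(1 − e^−2) = 21.0%. Before 2002 it is (1 − e^−0.2)/(1 − e^−1) = 28.7% to (1 − e^−0.4)/(1 − e^−2) = 38.1%. The documents do not support these as the bias in the study. They describe one worst-case entrant with no capture, and the rerun removes all of that time.

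Third, nothing in the documents shows that any practice left the network before 2018. The protocol is dated December 2018, so practices still contributing at extraction would cover the whole window. This stands too: the end-side gap is a flaw in the rule, not a demonstrated loss.

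Two wording points carry less weight. Requiring patients to be contributing to the database may suggest active contribution, but it is an inclusion condition and does not truncate person-time. Practice registration might mean the practice's own registration with the network, but the natural reading is the patient's registration with the practice. The provider may already restrict data to usable periods, but the protocol does not say so.

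**Conclusion.** The point holds in a limited form. Followed as written, the rules count any unrecorded practice time as time at risk. This lowers the main-analysis rates and, on the start side only, the prevalence of code-defined comorbidities and prescriptions. Over the assumed range the understatement of the rate is 1-15%. The true size is unknown because the documents give neither the affected share nor the capture within it, and it could be negligible if practices recorded throughout.

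Three stronger conclusions are tempting but unsupported:
- The main relative comparison is biased. The set-stratified hazard ratio is largely protected, provided capture in any gap is alike for exposed people and controls. The simulation addresses the unadjusted ratio only.
- No VTE could be recorded in the affected time. Incomplete recording is not zero recording.
- Particular diseases are hit harder because more of their patients enter in 1998. The documents give no entry dates by disease.

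The 2004 rerun reduces the concern for early years. It does not reach practices that became usable after 2004 (the documents identify none), the end of follow-up, or the main-analysis figures.

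**What to change.** Make two additions to the follow-up definitions:
- Start: include among the dates of which the latest is taken the date from which the practice's coded record is usable (data-quality or contribution start date, whichever the network holds).
- End: include among the dates of which the earliest is taken the practice's last data collection date.

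Apply both to exposed people, to controls and to the 2004 rerun, and report the person-time removed so that readers can see how much was at stake. State also whether practice registration means the patient's registration with the practice.

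The cost is two protocol clauses, two practice-level dates from the data provider, and the loss of some early person-time. The change is cheapest before analysis; afterwards the rates and baseline tables would have to be rerun.

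### In the VTE predictors models, recent hospitalisation, fracture and the early post-operative risk of joint replacement are coded once at baseline; if their excess risk is short, their HRs are diluted and not comparable with those of persistent factors

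*Combined protocol and SAP*

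**What the plan says.** The section on baseline characteristics and VTE risk factors states: "Diagnostic codes will be used to define the presence of comorbidities at baseline". The list that follows runs from hypertension and diabetes to "recent hospitalisation, joint replacement, and fractures". It gives no time window for a recent admission and no look-back for the other two.

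The section on predictors of VTE then fits multivariable Cox models to weigh individual risk factors against each other in the diseased and control cohorts. Platelet count is the only covariate said to vary with time. The section does not say outright that the others stay fixed, but that is the natural reading of the two sections together.

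The study runs from 1 January 1998 to 1 January 2018, so one person can contribute up to 20 years. "Follow-up will end at the earliest of the study end-date (January 1, 2018), the date of patient transfer from an included practice", death or outcome; nothing ties its length to a risk window. No proportional-hazards check or early/late split is planned, and the only sensitivity analysis moves the start date to 2004.

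On purpose, the lay summary says the study will "identify which risk factors are most strongly associated with the increased risk", and the introduction says "we will further compare the influence of VTE risk factors on risk of VTE events in individuals with systemic inflammatory disorders".

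**The concern.** With a single flag at entry, someone admitted shortly before entry counts as exposed for all of follow-up, and someone who breaks a hip in year 3 counts as unexposed when the clot follows. If the excess hazard lasts weeks or months, the fitted HR averages it over years in which it is absent, and later episodes raise the hazard of the reference group. Both effects move the HR towards 1. Diabetes or chronic kidney disease suffers no such loss.

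A comparison of these HRs would then partly reflect how long each factor acts rather than how strongly. This matters because the lay summary wants the results to help identify targets for reducing risk, and the introduction itself names fractures and surgery among the known VTE risk factors.

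**Working it through.** The plan states no sample size, event count or effect size, so there is no figure of its own to reproduce. The question is what a baseline-coded Cox model estimates when the effect is time-limited.

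**Inputs.** From the documents: background rate λ = 3 per 1000 person-years (Introduction) and maximum follow-up of 20 years (Study design). Assumed: true HR 4 for w years after each episode and 1 otherwise; 10% flagged, with the window opening at entry; exponential drop-out at rate c, truncated at 20 years, chosen to give mean follow-up m of 5, 7 or 10 years; later episodes at r1 per year in flagged and r0 per year in unflagged people.

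**Hazards.**
- Flagged: h1(t) = λ[1 + (HR − 1)q1(t)], where q1 = 1 for t < w and 1 − exp(−r1·w) afterwards.
- Unflagged: h0(t) = λ[1 + (HR − 1)q0(t)], where q0 = 1 − exp(−r0·min(t, w)).

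**Coded HR.** This is exp(b), where b solves the large-sample score equation ∫[p·S1·G·h1·(1 − e) − (1 − p)·S0·G·h0·e]dt = 0, with e = p·S1·exp(b) / [p·S1·exp(b) + (1 − p)·S0]. Here p = 0.10, S1 and S0 are event-free survival, and G is the probability of not having dropped out.

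**Check by hand, no later episodes.** Coded HR ≈ 1 + (HR − 1)·A/m, where A = (1 − exp(−c·w))/c is the mean time spent in the window. For m = 7, c = 0.133:
- w = 0.25 gives A = 0.246 and 1 + 3 × 0.246/7 = 1.11 (exact 1.11).
- w = 1 gives A = 0.936 and 1 + 3 × 0.936/7 = 1.40 (exact 1.41).

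**Results, true HR 4.** Each cell is for mean follow-up 5/7/10 years. The last column is the duration of excess, in years, at which the coded HR equals 1.5; a shorter excess ranks below a persistent factor with HR 1.5.

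| Later episodes per year, flagged v unflagged | 3 months | 6 months | 1 year | 2 years | Duration giving 1.5 |
|---|---|---|---|---|---|
| none | 1.15/1.11/1.08 | 1.29/1.21/1.15 | 1.55/1.41/1.30 | 2.01/1.77/1.57 | 0.89/1.24/1.74 |
| 0.1 v 0.1 | 1.14/1.10/1.07 | 1.25/1.18/1.13 | 1.42/1.31/1.22 | 1.64/1.48/1.35 | 1.30/2.17/4.17 |
| 0.15 v 0.05 | 1.21/1.17/1.14 | 1.39/1.32/1.27 | 1.67/1.56/1.47 | 2.05/1.89/1.75 | 0.68/0.86/1.09 |
| 0.3 v 0.1 | 1.26/1.23/1.20 | 1.46/1.40/1.36 | 1.74/1.65/1.57 | 2.01/1.89/1.79 | 0.55/0.67/0.80 |

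Recurrence matters: at 10 years' mean follow-up the duration giving 1.5 is 4.17 years if later episodes are equally common in both groups (0.1 per year), but 0.80 years if flagged people have three times the rate (0.3 v 0.1).

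**Shorter follow-up.** For a 6-month excess with no later episodes, the coded HR is 1.67 at a mean of 2 years and 2.18 at 1 year.

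**Both factors in one model.** With transient HR 4, persistent HR 1.5 (30% prevalence), mean 7 years and 0.1 episodes per year in all, the fitted HRs are 1.10 and 1.50 for a 3-month excess, and 1.48 and 1.50 for 2 years.

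**Handling episodes close to the VTE.** Deleting episodes in the last d days before a VTE removes true exposed events. For a 91-day window and HR 4, about 4 × (1 − d/91) remains: 3.7, 3.4 and 2.7 for 7, 14 and 30 days. A simulation of 2,000,000 people gave 3.70, 3.34 and 2.61, against 4.06 with no rule. A lag applied to everyone's person-time gave 4.02, 3.98 and 3.96. That simulation assumed a constant HR within the window.

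**The case against.** The strongest defence is that a model headed as predictors may properly use what is known at entry, and its HRs are then valid as prognosis from entry. That stands, and it makes this a problem of interpretation rather than of invalid estimation.

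Second, the wording of the predictors section can also mean comparing one factor's HR between the diseased and control cohorts. That comparison is less affected, because the events are coded alike in both. This stands too, but the lay summary's aim of finding the most strongly associated factors does compare factors with each other.

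Third, every decisive input is assumed, and 20 years is a maximum. Entry is staggered and people transfer or die, so mean follow-up may be short and the dilution modest. This is correct.

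Fourth, joint replacement is a lasting state and a fracture may mark lasting frailty, so part of their association may persist. This narrows the point to recent hospitalisation, fracture and the early post-operative risk of joint replacement.

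A reader might infer that the ranking of acute and persistent factors will be reversed. The documents do not support that. They give no duration of risk, and the table shows the order preserved in many plausible settings, particularly when flagged people have more later episodes.

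**Conclusion.** The point holds in a conditional form. As the plan is naturally read, short-lived effects in the predictors models are pulled towards 1 and are not on the same footing as persistent ones. For a true HR of 4 lasting 3 months, the coded HR is about 1.07 to 1.26 at 5 to 10 years' mean follow-up. It falls below a persistent HR of 1.5 when the excess lasts less than roughly 0.55 to 4.2 years, depending on follow-up and on later episodes. Apart from the background rate and the 20-year limit, all inputs are assumptions. If the excess is long or follow-up short, the effect is small.

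A reader might extend this to the disease-versus-control HRs. The documents do not support that: admissions and fractures after entry may lie on the path from disease to VTE, so adjusting for baseline status is defensible there.

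The medication window is a separate matter. Prescribing is defined by "an issued prescription in the three months preceding or one month after the date of diagnosis", while the exposed cohort takes "all individuals with an existing or incident diagnosis of IBD, RA or PsA", so for some people that window can precede cohort entry by years. That is a misalignment of dates and adds no weight here.

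The change should be made before analysis, but the study does not fail without it.

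**What to change.** In the predictors models only:

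- Add a supplementary start-stop Cox model beside the baseline-coded one. Fix in advance the risk windows for dated fractures, joint replacements and recorded admissions.
- As a sensitivity analysis for reverse causation, start each window after a short lag applied equally to all person-time. Do not delete episodes close to the VTE date.
- Describe the baseline-coded HRs as prognosis at entry, and do not rank acute against persistent factors from them.
- Treat time-updated steroids and hormones as optional, because time-updated steroid use in particular may be confounded by disease flares.

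Leave baseline adjustment in the disease-versus-control models as it is.

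The cost is additional programming, with a method the plan already applies to platelet count. There are two further downsides. The data source section says "All RCGP RSC registered practices have electronic laboratory links" but describes no hospital linkage, so admission dates may be incomplete. A lag also drops the earliest, possibly highest-risk, days of each window. If admission dates prove unusable, the change in wording alone still prevents the misleading comparison at almost no cost.
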